## 2.4. Safety Objective

The safety objective is to assess the safety and tolerability of voxelotor compared to placebo based on AEs, clinical laboratory tests, physical examinations, vital signs, and other clinical measures (eg, discontinuations due to AEs, dose reductions).

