## 3.1.3.4. Safety Endpoints

The safety endpoints include assessments of AEs, clinical laboratory parameters, physical examinations, and vital signs.

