## 3.2. Duration of Study Participation and of the Study

The approximate study duration for an individual participant includes the Screening Period (within 28 days), a Run-in Period of 2 weeks, a Randomized Treatment Period of 12 weeks, an Open-label Treatment Period of a minimum of 12 weeks, and a Follow-up Period/EOS visit (4 weeks [± 7 days] after the last dose of study drug). From Screening through Follow-up, total participation in this study for an individual participant may last from approximately 31 weeks to up to 34 weeks, except for participants who continue to receive voxelotor beyond 12 weeks in the Open-label Treatment Period (see below). Participants will continue to be followed for efficacy and safety through at least the primary endpoint visit (Week 12) regardless of treatment discontinuation.

Participants who have completed 12 weeks in the Open-label Treatment Period may continue to receive voxelotor as long as they continue to receive clinical benefit that outweighs risk as determined by the Investigator or until the participant has access to voxelotor from an alternative source (eg, through a clinical OLE study sponsored by Pfizer, commercialization of the product, or a managed access program).

Participants who choose not to continue voxelotor after 12 weeks in the Open-label Treatment Period will be followed for 4 weeks after the last dose of treatment and instructed to return to the site to complete the EOS visit (Visit 16-B, Appendix 1).

The study will end when the last participant's last visit occurs.

For participants who terminate the study prior to their last visit, refer to Section 3.3.1.

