## 8.2. Summary of Study Conduct

The number of participants randomized will be tabulated by country, study site, and treatment group. Participant disposition (the number of participants randomized, receiving at least 1 dose of study treatment, completing the study through the 12-week blinded Randomized Treatment Period, completing the study through the Open-label Treatment Period and Follow-up Visit) will be summarized by treatment group. Reasons for early discontinuation from study treatment and early discontinuation from the study will be summarized. Important protocol deviations will be listed and evaluated for potential impact on the interpretation of study results.

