## 2.2. Study Objectives and Endpoints

Туре	Objective	Endpoint
Primary	Primary	Primary
Efficacy	Characterize the effect of voxelotor and SOC (standard of care) compared to placebo and SOC on leg ulcer healing in participants ≥ 12 years of age with SCD by Week 12	The proportion of participants achieving resolution of the target ulcer(s), CCI  during the 12-week  Randomized Treatment Period. CCI
Secondary	Secondary	Secondary
Efficacy	Characterize the effect of voxelotor and SOC compared to placebo and SOC on secondary endpoints	
 
Time (in days) to resolution of target ulcer(s) up to Week 12
 
Change in total surface area(s) of target ulcer(s) at Week 12
 
Incidence of new ulcers by Week 12
 

Exploratory	Exploratory	Exploratory
Efficacy	Characterize the effect of voxelotor and SOC compared to placebo and SOC on exploratory endpoints	
 
Proportion of participants achieving resolution of target ulcer(s) by Week 24
 
Time (in days) to resolution of target ulcer(s) up to Week 24
 
Change from baseline in total surface area of target ulcer(s) over time up to Week 24
 

[figure not shown]
Туре	Objective	Endpoint
		Correlation between change in Hb and target ulcer(s) healing at Week 12 and Week 24  Correlation between change in hemolytic parameters (% reticulocytes, indirect bilirubin, LDH) and target ulcer(s) healing at Week 12 and Week 24  Health-related quality of life (HRQOL) using patient-reported outcome (PRO) measures, when available (pending translation and cultural validation requirements)  Change from baseline in PRO HRQOL measures: PROMIS-37 v2.0 Pediatric Profile/PROMIS-43 v2.1 at Week 12 and Week 24  Change from baseline in pain level linked to target ulcer(s) assessed by VAS at Week 12 and Week 24  Patient Global Impression of Change (PGI-C) score at Week 12 and Week 24  Clinician Global Impression of Change (CGI-C) score at Week 12 and Week 24
Safety	Assess the safety and tolerability of voxelotor compared to placebo	
 
AEs
 
Clinical laboratory tests
 
Physical examinations
 
Vital signs
 
Other clinical measures (eg. discontinuation due to AEs, dose reductions)
 

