## 6.5.2. Study Conduct and Participant Disposition

- The below participant population will be summarized by treatment group.
  - ITT Population.
  - Safety-Evaluable Population.
- Participant disposition (eg, discontinuation from study, reason for discontinuation, completed study, and ongoing) will be summarized by treatment group at Week 12 and 24.
- Actual exposure to study drug will be summarized by treatment group at Week 12 and 24.
- Important protocol deviations will be summarized by treatment group.

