#### 6.6.1. Adverse Events

SCD-related adverse events, defined as MedDRA PTs of sickle cell anaemia with crisis, acute chest syndrome, pneumonia, priapism (male participants only), splenic or hepatic sequestrations, stroke, and osteonecrosis, are included in the summary. Non-SCD-related adverse events are all other adverse events. The TEAEs/TESAEs and treatment-related AEs/SAEs will be displayed by SCD-related and non-SCD-related.

The total number and percentage of subjects with TEAEs will be presented by system organ class and preferred term by treatment group. TEAEs will be presented by severity (CTCAE grade or protocol defined severity). TEAEs will be tabulated presenting the system organ class alphabetically and within each system the preferred term will be presented by treatment group. The total number and percentage of subjects discontinued from study due to AEs will by presented by treatment group.

The frequency of subjects who experience each TEAE or treatment-related AE will be determined as follows: A subject experiencing the same AE multiple times will only be counted once for the preferred term. Similarly, if a subject experiences multiple AEs within the same system organ class, that subject will be counted only once for that system. If changes in the severity of an AE are recorded in the eCRF, only the most severe incidence of the AE will be counted. If a subject experiences multiple occurrences of a TEAE, only the related event or the worst severity (analysis dependent), will be counted for each subject within each system organ class or preferred term for the summaries of treatment-related AEs.

Missing onset dates will be imputed as previously outlined in Section 5.3.2 as required to determine treatment-emergent events. Should an event have a missing severity or relationship to study medication, then the severity or relationship, respectively, will be classified as missing for summary tabulation purposes.

Listings of AEs leading to discontinuation of the study, SAEs and deaths, if any, will be provided.

Listing of all AEs, including AEs occurred after 28 days of the last treatment date.

Deaths and SAEs will be listed and incidence of SAEs (all causalities and treatment-related) will be summarized by system organ class and PT by treatment group.

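### SAP 6.6.1 counts only AE-driven departures from the study, so AE-driven stops of study drug may be understated and dose reductions are summarised nowhere, although SAP 2.2 names both as safety endpoints

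*SAP*

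**What the plan says.** **What is to be measured.** The endpoint table in SAP 2.2 includes, under safety, "Other clinical measures (eg. discontinuation due to AEs, dose reductions". Protocol 2.4 names the same items in the safety objective: "other clinical measures (eg, discontinuations due to AEs, dose reductions". The protocol's own endpoint list (3.1.3.4) does not: "The safety endpoints include assessments of AEs, clinical laboratory parameters, physical examinations, and vital signs".

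**What is to be reported.**
- SAP 6.6.1, count: "The total number and percentage of subjects discontinued from study due to AEs will by presented by treatment group".
- SAP 6.6.1, listing: "Listings of AEs leading to discontinuation of the study, SAEs and deaths, if any, will be provided".
- SAP 6.5.2, disposition: "Participant disposition (eg, discontinuation from study, reason for discontinuation, completed study, and ongoing". It also summarises actual exposure by treatment group.
- SAP 3.5.3, the section on other safety endpoints, covers physical examination and vital signs only.
- Protocol 8.2: "Reasons for early discontinuation from study treatment and early discontinuation from the study will be summarized". SAP 2.1 declares no modification to the protocol's analysis plan.

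**What happens after a participant stops drug.** Protocol 3.2 continues follow-up for efficacy and safety "through at least the primary endpoint visit (Week 12) regardless of treatment discontinuation". Protocol 3.3.2.2, where adverse events are a listed reason for stopping treatment, calls for an EOS/Early Termination visit about 28 days (±7) after the last dose. Protocol 5.7.3 (chronic transfusion) and 5.7.4 (acute hepatitis or HIV) use the same visit.

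**The concern.** Tolerability is to be compared with placebo. The usual measures are how many participants stop, interrupt or reduce the drug because of an adverse event. The SAP names two of these as endpoints and then specifies a by-arm count of something else: leaving the study because of an adverse event. In a trial that intends to follow people after they stop drug, the two can diverge. If voxelotor led to more AE-driven drug stops or reductions, the specified outputs could fail to show it. The comparison needs to be readable in this trial, because the SAP introduction records that dosing was paused on 10 May 2024 over the number of deaths and the study was terminated on 25 September 2024.

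**Working it through.** There is no planned figure to reproduce. The check sets each stated measure against the outputs and then works through two rules.

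**1. Measure against output**

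| Measure | Specified in the SAP | Elsewhere |
|---|---|---|
| Left the study because of an AE | 6.6.1, count and listing | – |
| Stopped drug because of an AE | No count or listing | Protocol 8.2: reasons for stopping treatment |
| Dose reduced | None | None |
| Dose held | None; shortens actual exposure | None |

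**2. What the exposure summary can show.** SAP 2.3.3 defines actual exposure in weeks as the sum over dosing records of (end − start + 1) × I, divided by 7. I is 0 for a 0 mg dose and 1 for any other dose. For assumed dosing records over 84 days:
- Full dose throughout: 84/7 = 12.0 weeks.
- One tablet fewer from Day 15: (14 + 70)/7 = 12.0 weeks.
- Five-day hold, Days 15 to 19: (14 + 0 + 65)/7 = 11.3 weeks.
- Stopped after Day 28: 28/7 = 4.0 weeks.

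A reduction is invisible. A hold or a stop shortens exposure, but neither its cause nor the number of participants affected is shown.

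**3. When the Early Termination visit falls.** Under Protocol 3.3.2.2 the visit is at the last dose day + 28, with a window of ±7 days. Week 12 is Day 84.
- Last dose Day 28: visit at Day 56 (49 to 63).
- Last dose Day 42: visit at Day 70 (63 to 77).
- Last dose Day 56: visit at Day 84 (77 to 91).

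For any stop before Day 56, the nominal visit precedes Week 12. A site that treats that visit as the end of participation may record a study discontinuation. A site following Protocol 3.2 keeps the participant in the study. The same clinical event can therefore be inside or outside the SAP 6.6.1 count.

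**4. Possible size.** The shortfall equals the number of AE-driven drug stops not also recorded as leaving the study because of an AE. As a purely assumed example, take 4 such stops in an arm of 40, a true 10%. The count shows 4/40 = 10%, 2/40 = 5% or 0/40 = 0% if none, half or all of them lack that record. The documents do not say where in this range the trial would fall.

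**The case against.** The strongest reply is that drug stops are not lost. Protocol 8.2 commits to summarising reasons for stopping treatment separately from reasons for leaving the study, and SAP 2.1 changes nothing. The disposition list in SAP 6.5.2 is illustrative and excludes nothing. This stands in part: a reader might infer that AE-driven drug stops go wholly uncounted, and the documents do not support that. But the SAP, which sets out the detailed methodology, omits the item without declaring a change. A table of reasons would also not identify the adverse events, and it would not cover dose reductions.

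Second, a reader might infer that the protocol uniformly keeps drug stoppers in the study to Week 12, so that the count must show zero for them. It does not. Protocol 3.3.2.2, 5.7.3 and 5.7.4 point the other way. Even someone who stays to Week 12 may leave later and be counted then, because SAP 6.6.1 has no Week 12 cut-off and the safety period in SAP 2.3.2 runs to end of study.

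Third, serious events, deaths, severity and treatment-related events are all reported, and SAP 6.6.1 adds a listing of all AEs. That is correct, so the dosing pause does not imply that deaths are hidden. However, the SAP does not say that the listing shows the action taken with study drug, and a listing is not a by-arm comparison.

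Finally, the endpoint status rests on SAP 2.2, where the items are given as examples. Protocol 3.1.3.4 omits them.

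**Conclusion.** The point holds as a mismatch between stated safety endpoints and specified outputs. For discontinuation due to AEs, the SAP's only count and dedicated listing capture leaving the study, a different event, and the SAP does not carry forward the summary in Protocol 8.2. The count can understate AE-driven drug stops. The amount is undetermined, because it depends on which protocol passage a site follows and on the reason recorded. For dose reductions the gap is complete: neither document plans a summary, and the exposure formula cannot reveal them.

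This is a reporting gap that should be closed before the final analysis. The percentages above rest on an assumed number of stops and should not be read as an estimate. Sample size, power, alpha and the efficacy analyses are unaffected.

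**What to change.** - **SAP 6.6.1:** tabulate and list by treatment group, for the randomised and open-label periods, TEAEs leading to (a) permanent discontinuation of study drug and (b) dose reduction or interruption. Keep study discontinuation as a separate row.
- **SAP 6.5.2:** add the reasons for treatment discontinuation required by Protocol 8.2, with the sponsor's dosing pause as its own category so that it is not mixed with individual intolerance.
- **Protocol:** reconcile 3.2 with 3.3.2.2, 5.7.3 and 5.7.4 on what follows a drug stop, and state how such participants were recorded in disposition.

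The cost is SAP wording and a few extra tables. Protocol 5.1.2 already requires every dose modification to be recorded in the eCRF, and Protocol 7.2.1 requires the same for the AE behind a permanent or temporary stop.

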### 7.2.5. Worsening of Sickle Cell Disease

SCD-related AEs that are common complications associated with the study participant's SCD may not be considered related to voxelotor unless judged by the Investigator to have worsened in severity and/or frequency or changed in nature during the study. SCD-related AEs include: SCD with vaso-occlusive pain crisis, acute chest syndrome, pneumonia, priapism, splenic or hepatic sequestrations, stroke, and osteonecrosis (Kato, 2018).

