#### On-treatment period:

On-treatment period is defined as the time from the first dose of study drug through minimum of 28 days + last dose of study drug and the date of study completion/discontinuation.

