## Actual exposure to study drug

Actual exposure to study drug is defined as the number of weeks from initiation of study drug to the last date of dosing of study drug which excludes days where treatment was

entirely missed or intermittently stopped as recorded in the CRF. Duration of study drug exposure is calculated as follows:

$$\frac{\sum_{i=1}^{n} (End \ Date \ of \ Dose_{i} - Start \ Date \ of \ Dose_{i} + 1) \times I_{Dose_{i}}}{7}$$

where n is the number of dose modifications during the study and

$$I_{Dose_i} = \begin{cases} 0 \text{, if treatment dose } i = 0 \text{ mg} \\ 1 \text{, if treatment dose } i \neq 0 \text{ mg'} \end{cases} i = 1, 2, ..., n.$$

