## 3.5. Safety Endpoints

#### 3.5.1. Adverse Events

MedDRA will be used to code all AEs (non-serious and serious) with respect to system organ class and preferred term (PT) using most current version of the MedDRA dictionary.

TEAE is defined as an AE that occurs or worsens during the on-treatment period as defined in Section 2.3.3.

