## 6.4.2. Subset analysis for safety endpoints

Safety subgroup analyses will be performed on safety analysis set for SCD-related TEAEs and TESAEs in the randomized treatment period on the following subgroups.

- Malaria
  - a. Subjects with at least one TEAE of Malaria by Week 12 (Yes, No)
  - Subjects with at least one TEAE of Malaria by Week 24 (Yes, No)
- Change from Baseline in Hemoglobin at Week 12 (< 0 g/dL, 0-1 g/dL, >1 g/dL)
- Hemoglobin at Week 12 (< 7 g/dL, >=7 g/dL and <9 g/dL, >=9 g/dL)
- Number of VOCs in the past 12 Months (0 VOCs, >=1 VOCs)
- Number of VOCs in the past 12 Months (1 VOC, >=2 VOCs)
- Country (Nigeria, Kenya, Brazil)

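### The SAP counts each participant once per preferred term and plans no event count or rate for SCD-related events, so a rise in recurrent crises is shown diluted, and a rise confined to repeats of no greater severity or seriousness does not appear in the all-causality percentages

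*SAP*

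**What the plan says.** SAP 6.6.1 presents the number and percentage of participants with TEAEs by system organ class and preferred term. Its counting rule is "A subject experiencing the same AE multiple times will only be counted once for the preferred term". The same rule applies to system organ classes and to treatment-related events, and by severity only the worst occurrence is kept. SCD-related events are a fixed list of preferred terms headed by sickle cell anaemia with crisis. The SCD-related and non-SCD-related display splits these same tables.

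SAEs are summarised by incidence, and a separate sentence in 6.6.1 promises counts and percentages without saying whether the counts are of events or participants. Individual repeats survive in listings: "Listing of all AEs, including AEs occurred after 28 days of the last treatment date".

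For timing, "TEAE is defined as an AE that occurs or worsens during the on-treatment period", and that period runs from first dose to the earlier of 28 days after last dose and study completion or discontinuation (SAP 2.3.3). Exposure is reported separately: "Actual exposure to study drug will be summarized by treatment group at Week 12 and 24". Actual exposure leaves out days "entirely missed or intermittently stopped as recorded in the CRF".

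Protocol 7.2.5 lets common SCD complications be treated as unrelated to study drug "unless judged by the Investigator to have worsened in severity and/or frequency or changed in nature during the study". SAP 6.4.2 uses the number of vaso-occlusive crises in the previous 12 months as a safety subgroup factor.

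**The concern.** Crises recur, and a participant with one crisis contributes the same to the preferred-term row as a participant with five. The protocol names worsened frequency as a ground for relatedness, but that judgment is made participant by participant. No planned table compares on-study frequency between arms.

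This matters more here than in most trials of this size. SAP Section 2 records that dosing was paused because of the overall number of deaths and that the study was then terminated. Version 4 was revised for the final report and added safety subgroups on SCD-related events. SCD safety by arm is thus a central question for that report.

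Time at risk also varies. The open-label safety period runs to end of study, continuation past 12 weeks was optional, and dosing was paused on a calendar date. Percentages without participant-time do not allow for this.

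**Working it through.** **Planned outputs.** SAP 6.4.2, 6.5.2 and 6.6 to 6.6.3 contain no event count labelled as such, no participant-time denominator and no event rate. Protocol 8.5 speaks of the frequency of AEs without giving a unit. SAP 6.6.1 defines frequency as the frequency of subjects.

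**Inputs.** From the documents: 40 participants per arm (SAP 2.3.1) and 84 days to Week 12. Assumed, because the documents give no crisis rate: placebo rate 1, 2, 4 or 6 per year; gamma-Poisson dispersion k = 0, 0.5 or 1; full follow-up. There is no figure in the plan to reproduce.

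**1. General doubling.** With T = 84/365.25 years and mu = rate × T:
- expected crises per arm = 40 × mu
- P(at least one) = 1 − (1 + k·mu)^(−1/k), or 1 − exp(−mu) when k = 0
- share of crises not counted = 1 − P/mu

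At 2 per year and k = 0.5, placebo mu = 0.460 and P = 1 − 1.230^(−2) = 0.339. Voxelotor mu = 0.920 and P = 1 − 1.460^(−2) = 0.531. The true rate ratio is 2; the participant ratio is 0.531/0.339 = 1.57.

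| Placebo rate per year (k = 0.5) | Expected crises, placebo vs voxelotor | Participants in the planned table | Participant ratio | Voxelotor crises not counted |
|---|---|---|---|---|
| 1 | 9.2 vs 18.4 | 7.8 vs 13.6 | 1.73 | 26% |
| 2 | 18.4 vs 36.8 | 13.6 vs 21.2 | 1.57 | 42% |
| 4 | 36.8 vs 73.6 | 21.2 vs 29.1 | 1.37 | 60% |
| 6 | 55.2 vs 110.4 | 26.0 vs 32.9 | 1.27 | 70% |

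Over the full grid the participant ratio runs from 1.25 (6 per year, k = 0) to 1.79 (1 per year, k = 0). The uncounted voxelotor share runs from 20% (1 per year, k = 0) to 73% (6 per year, k = 1).

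**2. Rise in repeats only.** If 16 participants per arm have a crisis, one each on placebo and three each on voxelotor, there are 16 vs 48 events. If no repeat is more severe or serious than the first, the planned row reads 16 (40%) vs 16 (40%).

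A less extreme version was simulated: gamma frailty with k = 0.5, time to first crisis unchanged, and repeats at two or three times the placebo rate. The participant percentages are equal by construction.

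| Placebo rate per year | Repeats | Expected crises | Rate ratio (approximate 95% CI, 40 per arm) |
|---|---|---|---|
| 2 | doubled | 18 vs 23 | 1.27 (0.60–2.65) |
| 4 | doubled | 37 vs 52 | 1.42 (0.80–2.52) |
| 2 | tripled | 18 vs 28 | 1.53 (0.72–3.25) |
| 4 | tripled | 37 vs 68 | 1.85 (1.03–3.30) |

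**3. The limit on invisibility.** More repeats also give a participant more chances of a serious one. In the same model at 4 per year with repeats tripled, participants with at least one serious crisis rise from 9.1 to 12.6 of 40 if 30% of crises are serious. The rise is 6.4 to 9.6 at 20% and 13.5 to 16.5 at 50%. These proportions are assumed. The TESAE table then moves, by a ratio of about 1.2 to 1.5.

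**4. Precision of an added rate ratio.** Var(log RR) = (1/mu0 + k)/40 + (1/mu1 + k)/40. For a true general doubling at 2 per year and k = 0.5 this is 0.067 + 0.040 = 0.107, so the interval is 2 × exp(±1.96 × 0.326), about 1.05 to 3.8. At 1 per year it is about 0.85 to 4.7, and at 4 per year about 1.2 to 3.3.

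**5. Rebuilding a rate from planned outputs.** The AE listing and the Week 12 exposure summary allow an approximate hand calculation. The windows differ: TEAEs can fall up to 28 days after the last dose, while actual exposure drops missed and stopped days.

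**The case against.** Participant-level incidence is a valid main display for adverse events, and the plan should keep it.

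A reader might infer that the SAP hides any increase in crises. The documents do not support that. A general rise shows as more participants affected; at 2 per year a doubling reads 34% vs 53%, which is diluted but plain. With the mix of severity per crisis unchanged, extra repeats also raise worst grades and the number of participants with a serious crisis, and both are tabulated. Only repeats no more severe or serious than the participant's earlier ones leave the percentages flat, and nothing in the documents suggests that voxelotor acts on repeats alone.

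A reader might also infer that no planned output could contain event counts. That is not established, because the unit of the SAE counts in SAP 6.6.1 is open. Even if they are events, they would not cover non-serious crises or supply participant-time.

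Nor do the documents show that crises rose or differed by arm. They report no crisis counts, and the pause is attributed to deaths overall. The prior-crisis subgroup is a baseline factor and does not make on-study crisis count a planned outcome.

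Two practical objections stand in part. The listing holds the data, but it is not a comparison by arm. Protocol 7.2.4 allows worsening of a pre-existing condition to be recorded with a descriptor such as more frequent episodes, so one AE record need not be one crisis. Event counts therefore need an episode rule.

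The treatment-related tables may pick up part of a rise, but they depend on individual judgment and also count each participant once.

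**Conclusion.** The concern holds in limited form and is best labelled a cheap improvement. The once-per-term rule dilutes a general rise in crises: under the assumed rates, a true doubling is shown as a ratio of about 1.25 to 1.79, with 20% to 73% of voxelotor-arm crises not counted. The narrower repeat-only rise described above is missed by the all-causality TEAE and TESAE percentages.

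These sizes rest on assumed rates and dispersion, the planned 40 per arm and complete 84-day follow-up. The reading of the counting rule does not depend on them. At this sample size a rate table would display a repeat-only rise but would usually not establish it, so its value is descriptive.

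**What to change.** In SAP 6.6.1, keep the participant-level tables and add one descriptive table by treatment group and reporting period. For SCD-related TEAEs and TESAEs overall, and for sickle cell anaemia with crisis, give:

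- number of events
- participant-years on treatment, using the SAP 2.3.3 on-treatment period within each reporting period, so that the denominator matches the TEAE window
- events per participant-year

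State the episode rule, for example distinct eCRF onset dates, with records that describe only worsened frequency flagged. State whether the SAE counts are events or participants. A voxelotor to placebo rate ratio with 95% CI for the randomized period is optional; it should be descriptive, without a p-value.

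The cost is SAP wording, an episode rule and one extra table from AE and dosing dates already collected. No efficacy analysis changes. SAP version 4 is dated after the last participant's last visit, so the table should be labelled with the date it was added.

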#### 2. INTRODUCTION

This SAP provides the detailed methodology for summary and statistical analyses of the data collected in Study GBT440-042 for the final CSR after last subject last visit (LSLV). This document may modify the plans outlined in the protocol, however, any major modifications of the primary endpoint definition or its analysis will also be reflected in a protocol amendment. Statistical analyses will be performed using cleaned case report form (CRF) data as well as non-CRF data (i.e., blood samples data and banked biospecimens).

The administration of the study intervention was voluntarily paused by the Sponsor on 10 May 2024 due to the overall number of deaths observed in the study. The decision was made by the sponsor to terminate the study on 25 September 2024 and the LSLV was on 22 October 2024.

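### Dosing was paused because of deaths, but the SAP plans only a listing of deaths: no all-cause death table by randomised arm and no death rate tied to person-time

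*SAP*

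**What the plan says.** SAP Section 2 records that dosing was "voluntarily paused by the Sponsor on 10 May 2024 due to the overall number of deaths observed in the study", that the sponsor terminated the study on 25 September 2024, and that "the LSLV was on 22 October 2024". SAP Section 1 dates version 4 at 16 December 2024, after all three events. Its change log adds the statement about the pause and a set of safety subgroups, but no summary of deaths.

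SAP 6.6.1 mentions deaths twice, both times as a listing: "Listings of AEs leading to discontinuation of the study, SAEs and deaths, if any, will be provided" and "Deaths and SAEs will be listed and incidence of SAEs (all causalities and treatment-related) will be summarized by system organ class and PT". It also plans a listing of all AEs that includes those more than 28 days after last treatment.

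TEAEs are tied to the on-treatment period in SAP 2.3.3, which runs from first dose "through minimum of 28 days + last dose of study drug and the date of study completion/discontinuation". Protocol 3.2 continues follow-up for efficacy and safety to at least Week 12 whether or not treatment has stopped. The safety objective (Protocol 2.4, SAP 2.2) is a comparison of voxelotor with placebo.

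**The concern.** Mortality is the reason that the SAP itself gives for the pause, and the safety objective is comparative. One would expect a plan finalised after those events to say how deaths will be compared between the randomised arms. It names listings and leaves the comparison to whoever reads them.

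Two things are at stake. First, if nothing is specified, the period, population, denominator and interval for the death comparison will be chosen with the data in hand. Second, the 28-day rule removes some randomised follow-up from the treatment-emergent tables. The participants affected are those who stopped treatment early, a group whose deaths a by-arm comparison should not lose.

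**Working it through.** The plan states no figure for deaths, so there is none to reproduce. The check has three parts.

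**1. Which by-arm outputs could carry a death?**
- SAE incidence (SAP 6.6.1): "incidence of SAEs (all causalities and treatment-related) will be summarized by system organ class and PT by treatment group". Fatal and non-fatal events are not separated. The sentence is not expressly limited to treatment-emergent events, so a late fatal SAE might be counted, but it would not be shown as fatal.
- TEAEs by severity (SAP 6.6.1): Grade 5 is fatal (Protocol 7.1.2), but the table covers treatment-emergent events only.
- Disposition with reason for discontinuation at Weeks 12 and 24 (SAP 6.5.2): death is not named as a category.
- Type of censoring in the time-to-resolution analysis (SAP 5.2.3): death is given as an example, but this reaches only participants whose target ulcers are unresolved, up to Week 12.
- Exposure by treatment group at Weeks 12 and 24 (SAP 6.5.2): summarised, but not used as a denominator for deaths.

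None of these is defined as a complete all-cause count by randomised arm, and none gives a difference or rate for deaths.

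**2. What does the 28-day rule leave out?**
- Randomised period: Week 12 is Day 84. A last dose on Day d closes the window on Day d + 28, which is before Day 84 when d < 84 − 28 = 56. For example, a last dose on Day 14 closes the window on Day 42, leaving 84 − 42 = 42 days of randomised follow-up outside it.
- After the pause: for a last dose on 10 May 2024, the window closes on 7 June 2024. From 10 May to 22 October is 165 days, so at most 165 − 28 = 137 days fall outside. This is a maximum. It needs a participant dosed up to the pause date and still followed at the last visit of the study. Under Protocol 3.3.2.2 the visit after stopping is due at 28 ± 7 days, which would leave at most about 7 days outside. Individual study-end dates are not given.

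**3. How precise would a death table be?**
The documents give no death counts, so this is illustrative. Assume the planned 40 per arm (SAP 2.3.1) and full 12-week follow-up.
- Person-years per arm: 40 × 84 / 365.25 = 9.2.
- 0 deaths in 40: exact 95% upper limit 1 − 0.025^(1/40) = 8.8%. As a rate, −ln(0.025) / 9.2 = 40 per 100 person-years.
- 2 deaths in 40: 0.6% to 16.9%, or 2.6 to 79 per 100 person-years.
- 5 deaths in 40: 4.2% to 26.8%, or 18 to 127 per 100 person-years.
- Smallest imbalances with two-sided Fisher p < 0.05: 6 v 0 (p = 0.026), 8 v 1 (p = 0.029), 9 v 2 (p = 0.048).

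The table is feasible but imprecise.

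**The case against.** The strongest reply is that the information is there. Deaths are listed, all AEs are listed including late ones, and with about 80 participants anyone can count deaths by arm. If the CRF has death as a reason for leaving the study, the Week 12 disposition table may come close to a full count. This stands in part. A reader might infer that the mortality question cannot be answered, or that deaths are not counted by arm anywhere. The documents support neither. Equally, exposure is summarised by arm, so time at risk is not absent; it is only not linked to deaths.

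A reader might also pool the periods: with full follow-up to Week 24, voxelotor would have (40 × 168 + 40 × 84) / 365.25 = 27.6 person-years against 9.2 on placebo, and crude counts would mislead by a factor of three. That describes no planned table. SAP 2.3.2 reports the randomised and open-label periods separately, and the open-label period has no placebo group. Within the randomised period, planned time at risk is equal.

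It is also fair to say that the SAP cannot cure everything. Active AE and SAE collection under Protocol 7.2.1 ends 28 days after last dose, so later deaths may be incompletely captured. After Week 12 (Week 14 for some) no concurrent placebo group exists, whatever window is used.

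What the reply does not meet is the lack of any pre-specified comparison between randomised arms of the event that led to the pause.

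**Conclusion.** The point holds as a gap in pre-specified analysis, and it should be fixed. The SAP lists deaths but specifies no all-cause death table by randomised arm and no death rate with person-time. The partial by-arm outputs do not add up to one. The treatment-emergent tables omit deaths more than 28 days after last dose, including some within the randomised period when the last dose is before about Day 56; the AE and death listings are the outputs that expressly cover them. After the pause, at most 137 days per participant lie outside that window, and probably far fewer on the scheduled end-of-study visit.

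The precision figures assume 40 per arm with complete 12-week follow-up. They say nothing about the actual number of deaths or its direction, neither of which the documents give.

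**What to change.** In SAP 6.6.1, add:

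1. A table of all-cause deaths by randomised arm, from Day 1 to Week 12 (Week 14 for participants awaiting confirmation of resolution), regardless of treatment discontinuation. Give number and percentage, person-years, and the risk difference with a 95% CI (e.g. Newcombe).
2. A separate summary of open-label-period deaths through end of study, for the voxelotor and delayed-voxelotor groups, per 100 person-years with exact CI, split at 28 days after last dose. Label it descriptive and non-randomised, and note that active SAE collection ends 28 days after last dose, so later deaths may be under-recorded.

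Keep the listings. The cost is one or two extra tables, mostly from data already planned for listing, and the intervals will be wide. Showing that width is better than leaving the reader to judge the listings unaided.
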